3.7.2. Adverse Events

Adverse events (AEs) will be coded to the preferred terms (PT) of the Medical Dictionary for Regulatory Activities (MedDRA®). Summaries for induction period and for the complete study period will be presented separately and by system organ class (SOC), preferred term, and severity and/or relatedness, the number and percentage of subjects for whom events were reported.

Adverse events (AEs) are recorded from signing of the informed consent form through the final follow-up assessment. Adverse events observed prior to first dose are non-treatment emergent.

Treatment emergent adverse events are defined as follows for induction period and overall:

- TEAEs are AEs with onset on or after the first initiation of study drug up to the date of last dose of study drug + 28 days.

Only treatment-emergent AEs will be summarized in the tables.

An AE will be considered a treatment-emergent serious AE (TESAE) if it is a TEAE that additionally meets any SAE criteria.

If more than 1 AE is coded to the same preferred term for the same subject, the subject will be counted only once for that preferred term using the most severe and most related occurrence for the summarizations by severity and by relationship to study drug.

Summary tables will also be provided for Induction period and overall for subjects with:

- TESAEs by SOC and PT
- TEAEs leading to discontinuation of study drug by SOC and PT
- Drug related TEAEs by SOC and PT
- TEAEs by severity and by SOC and PT
- TEAEs resulting in death by PT

Listings of all AEs, SAEs, and AEs leading to discontinuation by subject will be presented.

An overall summary of adverse events will also be presented and will include the following summary lines: Any AE, Moderate or Severe AEs, AEs Related to Study Drug, Moderate or Severe AEs Related to Study Drug, Serious AEs, Serious AEs Related to Study Drug, AEs Leading to Premature Study Drug Discontinuation, AEs Leading to Temporary Interruption of Study Drug, and Deaths During Study.

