3.7.3. Additional Safety Assessments

3.7.3.1. Clinical Laboratory Parameters

Laboratory data, hematology, serum chemistry and urinalysis, will be summarized in terms of observed values and changes from baseline for induction period and overall. In addition, changes from baseline relative to normal ranges from the central lab (e.g., shifts from normal to abnormal high/low) will be summarized.

Summaries for laboratory parameters of special interest will also be presented, these will include:

- Neutrophils
- Leukoocytes
- Lymphocytes
- Hemoglobin
- Lipids [LDL cholesterol, HDL cholesterol, Cholesterol, and Triglyceride]
- Liver Function Test's [ALT, AST, Bilirubin]
- Creatinine
- Creatinine Kinase

The number and percentage of subjects with clinically abnormal lab values will also be summarized by timepoint for the following criteria:

- absolute neutrophil count of $< 1.0 \times 10^9/L$
- white blood cell count of $< 2.0 \times 10^9/L$
- absolute lymphocyte count of $< 0.5 \times 10^9/L$

A summary of maximum National Cancer Institute Common Terminology Criteria for Adverse Events (NCI-CTCAE) toxicity grade (Appendix 5.8) for postbaseline laboratory values through Week 8 and through Week 16.

Listings will flag laboratory values that are outside of normal range.

A listing of all abnormal lab values will be provided. Listings of subjects with any abnormal postbaseline laboratory values of CTCAE grade ≥ 2 will also be provided.

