3.7.3.3. Electrocardiograms

Descriptive statistics for ECG parameters (heart rate, RR interval, PR interval, QRS interval, QT interval, and QTcF) and changes from baseline values at each assessment time point to the end of study will be presented by treatment group. The QTcF will be calculated using the Fridericia correction.

Subjects without a postbaseline measurement for a given treatment period will be excluded from the summary statistics (e.g., denominator of the summary statistic) for that time point.

All recorded values for the standard 12-lead electrocardiogram parameters will be presented in a by-subject listing.

Categorical Analyses

The number (percentage) of subjects with absolute ECG values and change from baseline in the ranges shown in Table 10 will be presented in Electrocardiogram Categorical Summary by Visit and Time Point.

In addition, in the same summary, QTcF will also be summarized by the following categories, Normal (males < 430, females ≤ 450), Borderline (males (> 430, ≤ 450); females (> 450, ≤ 470)) and Prolonged (males > 450, females > 470).

Individual ECG data collected during the study will be presented in a listing. A separate listing of subjects with values of QTcF > 500 msec or an increase > 60 msec will be provided, as necessary.

Investigator Assessment of ECG Readings

The investigators’ assessment of ECGs as normal, abnormal and clinically significant, or abnormal but not clinically significant will be summarized for baseline and for each visit.

Table 10: ECG Interval Categories

Heart Rate (bpm)	Heart Rate Change from Baseline (bpm)	PR Interval (msec)	PR Percentage Change From Baseline (%)	QRS Interval (msec)	QT _c F (msec)	QT _c F change from Baseline (msec)
> 120	≥ 20	≥ 200	≥ 15	≥ 120	Males:	≤ 30
> 130	≥ 30	≥ 220	≥ 25		< 430	>30, ≤ 60
					≥ 430	> 60

[REDACTED]

[REDACTED]

[REDACTED]

[REDACTED]

[REDACTED]

[REDACTED]

[REDACTED]

[REDACTED]

[REDACTED]

[REDACTED]

[REDACTED]

[REDACTED]

[REDACTED]

[REDACTED]

[REDACTED]

[REDACTED]

[REDACTED]

[REDACTED]

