5.3. Adverse Event Start and End Date/Time Imputation Rules

Missing start date and times will be handled as follows:

- AE onset date completely missing:
 - If AE is not ongoing and AE onset date missing and AE end date missing, then impute AE onset as date/time of first dose.
 - Else if AE is not ongoing and AE onset date missing and AE end date not missing and date/time of first dose \leq AE end date, then impute AE onset as date/time of first dose of study drug.
 - Else if AE is not ongoing and AE onset date missing and AE end date not missing and AE end date is BEFORE first dose of study drug, then impute AE onset as AE end date YEAR and MONTH with 01 as the day and 00:00 as time.
 - Else if AE IS ongoing and AE onset date missing, then impute AE onset as date/time of first study drug dose.
- AE onset date has year and month only:
 - If AE onset date has year and month only and they are the year and month of first dose of study drug, then impute AE onset as date/time of first dose:
 - Else if AE onset date has year and month only and date/time of first dose is not missing, then impute AE onset as AE onset year and month with 01 as the date and 00:00 as the time.
- AE onset date has year only:
 - If AE onset date has year only and it is year of first dose of study drug, then impute AE onset as date/time of first dose of study drug.
 - Else if AE onset date has year only and date of first study drug dose is not missing and year of AE onset is NOT the year of first dose of study drug, then impute AE onset as Jan. 1 of the AE onset year and 00:00 as the time.
- AE onset missing (where it was not handled by the above cases):
 - If AE onset date is missing, then impute AE onset as date/time of first study drug dose.
- AE onset has complete date but missing time:
 - If AE onset date is a date only and is same as date of first study drug dose, then impute AE onset as date/time of first study drug dose:
 - Else if AE onset date is a date only and is NOT = date of first study drug dose, then impute AE onset as AE onset date with 00:00 as the time:

Missing end date and times will be handled as follows:

- AE end date - completely missing:

- If AE is not ongoing and both AE onset and AE end dates are missing, then impute AE end date as date/time of last study drug dose.
 - Else if AE is not ongoing and AE onset date not missing and AE end date missing AND AE onset date \leq date/time of last dose, then impute AE end date as date/time of last study drug dose.

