Calcium (mmol/L)	Decrease	[Albumin \geq 40 g/L or missing and calcium \geq 2.0 - <LLN]; or [Albumin < 40 g/L and (calcium - 0.8 x (albumin - 40)) \geq 2.0 - <LLN]	[Albumin \geq 40 g/L or missing and calcium \geq 1.75 - <2.0]; or [Albumin < 40 g/L and (calcium - 0.8 x (albumin - 40)) \geq 1.75 - <2.0]	[Albumin \geq 40 g/L or missing and calcium \geq 1.5 - <1.75]; or [Albumin < 40 g/L and (calcium - 0.8 x (albumin - 40)) \geq 1.5 - <1.75]	[Albumin \geq 40 g/L or missing and calcium <1.5]; or [Albumin < 40 g/L and (calcium - 0.8 x (albumin - 40)) <1.5]
Creatine Kinase	Increase	>ULN - \leq 2.5 xULN	>2.5 xULN - \leq 5.0 xULN	>5.0 xULN - \leq 10.0 xULN	>10.0 xULN
Creatinine	Increase	>ULN - \leq 1.5 xULN	>1.5 xULN - \leq 3.0 xULN	>3.0 xULN - \leq 6.0 xULN	>6.0 xULN
GGT	Increase	>ULN - 2.5 x ULN if baseline was normal; 2.0 - 2.5 x baseline if baseline was abnormal	>2.5 - 5.0 x ULN if baseline was normal; >2.5 - 5.0 x baseline if baseline was abnormal	>5.0 - 20.0 x ULN if baseline was normal; >5.0 - 20.0 x baseline if baseline was abnormal	>20.0 x ULN if baseline was normal; >20.0 x baseline if baseline was abnormal
Phosphate (mmol/L)	Decrease	\geq 0.8 - <LLN	\geq 0.6 - <0.8	\geq 0.3 - <0.6	<0.3
Potassium (mmol/L)	Increase	>ULN - \leq 5.5	>5.5 - \leq 6.0	>6.0 - \leq 7.0	>7.0
Potassium (mmol/L)	Decrease	\geq 3.0 - <LLN		\geq 2.5 - <3.0	<2.5
Sodium (mmol/L)	Increase	>ULN - \leq 150	>150 - \leq 155	>155 - \leq 160	>160
Sodium (mmol/L)	Decrease	\geq 130 - <LLN		125-129 mmol/L symptomatic; 120-124 mmol/L regardless of symptoms	<120
Triglycerides (mmol/L)	Increase	1.71 - \leq 3.42	>3.42 - \leq 5.7	>5.7 - \leq 11.4	>11.4

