3.7.3. Additional Safety Assessments

3.7.3.1. Clinical Laboratory Parameters

Laboratory data, hematology, serum chemistry and urinalysis, will be summarized in terms of observed values and changes from baseline. In addition, changes from baseline relative to normal ranges from the central lab (e.g., shifts from normal to abnormal high/low) will be summarized.

The number and percentage of subjects with clinically abnormal lab values will also be summarized by timepoint for the following criteria:

- absolute neutrophil count of $< 1.0 \times 10^9/L$
- white blood cell count of $< 2.0 \times 10^9/L$
- absolute lymphocyte count of $< 0.5 \times 10^9/L$

A summary of maximum National Cancer Institute Common Terminology Criteria for Adverse Events (NCI-CTCAE) toxicity grade (Appendix 5.3) for postbaseline laboratory values.

A listing of all abnormal lab values will be provided.

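### Three safety rules leave gaps or misclassify: asymptomatic sodium of 125-129 mmol/L is ungraded in both SAPs, Phase 2b section 5.3 makes some AEs that ended before dosing treatment-emergent, and a male QTcF of 430 msec has no category

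*SAP*

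**What the plan says.** **Sodium.** Phase 2b SAP section 5.8 and Maintenance SAP section 5.3 carry the same row for decreased sodium. Grade 1 runs from 130 up to the lower limit of normal, grade 2 is empty, grade 3 is "125-129 mmol/L symptomatic; 120-124 mmol/L regardless of symptoms", and grade 4 is below 120. Both SAPs use the table for a summary of maximum grade; in the Maintenance SAP (section 3.7.3.1) this is the "toxicity grade (Appendix 5.3) for postbaseline laboratory values". Phase 2b section 3.7.3.1 adds "Listings of subjects with any abnormal postbaseline laboratory values of CTCAE grade" 2 or higher.

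**AE onset.** Phase 2b SAP section 3.7.2 states that "TEAEs are AEs with onset on or after the first initiation of study drug up to the date of last dose of study drug" plus 28 days, and that AEs seen before first dose are not treatment-emergent. Section 5.3 then imputes missing onsets:
- Onset fully missing, AE not ongoing: if "AE end date is BEFORE first dose of study drug, then impute AE onset as AE end date YEAR and MONTH", taking the first of that month. The AE stays pre-dose.
- Onset with year and month only: if "they are the year and month of first dose of study drug, then impute AE onset as date/time of first dose". The end date plays no part.
- Onset with year only, same year as first dose: also set to first dose, again without the end date.

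**QTcF.** Section 3.7.3.3 of both SAPs defines Normal for males as below 430 msec and the next class as "Borderline (males (> 430, ≤ 450" msec).

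**The concern.** A grading table should give every abnormal value one grade, and worse values should not rank below milder ones. The sodium row fails this for asymptomatic results in one band. A subject whose worst sodium falls there can be missing from the graded output, while a subject with a milder value appears in it.

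The AE rule matters because AEs are recorded from consent, the screening period is Day -28 to -1, and screening includes an endoscopy with biopsies. Protocol section 7.1.1 counts complications of protocol-mandated procedures as AEs. Some AEs can therefore begin and end before the first dose. If one of these has an incomplete onset date, section 5.3 can place it under study drug or placebo, against the definition in section 3.7.2.

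**Working it through.** No sample size, power or alpha figure is involved. The check applies the rules literally.

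**Sodium.** The documents give no lower limit of normal, so 135 mmol/L is assumed for illustration.

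| Sodium (mmol/L) | Asymptomatic | Symptomatic |
|---|---|---|
| 134, 130 | 1 | 1 |
| 129, 127, 125 | none | 3 |
| 124, 120 | 3 | 3 |
| 119 | 4 | 4 |

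For an asymptomatic subject the grade goes from 1 (130) to none (127) to 3 (124). If results are reported with decimals, 129.5 and 124.5 also fall in no cell, with or without symptoms. The empty grade 2 cell is not in itself the fault. The low-potassium row is also empty at grade 2, but its grade 1 (3.0 and above) and grade 3 (2.5 to below 3.0) meet, so no value is lost.

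**AE onset.** Take a first dose on 20 June 2020 and an AE known to have ended on 10 June 2020.

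| Recorded onset | Imputed onset | Result |
|---|---|---|
| Fully missing | 1 June 2020 | not a TEAE |
| 1 June 2020 (complete) | none needed | not a TEAE |
| May 2020 | 1 May 2020 | not a TEAE |
| June 2020 | 20 June 2020 | TEAE; onset 10 days after its own end |
| 2020 | 20 June 2020 | TEAE; onset 10 days after its own end |

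The rule gives the right class when nothing is known about onset and the wrong class when the month or year of first dose is known.

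Section 5.2.2.1 of the Phase 2b SAP does not repair this. It covers partial start dates only for AEs already classed as TEAEs, which is circular where the start date decides the class, and it has no end-date check either. The Maintenance SAP has the same section 5.2.2.1 but no counterpart to the Phase 2b section 5.3 onset rules, so the explicit error is in the Phase 2b SAP only.

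**QTcF.** For males, below 430 is Normal and above 430 up to 450 is Borderline, so 430 is in neither. For females, Normal is up to and including 450 and Borderline starts above 450, so those classes meet.

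**The case against.** The strongest reply is that each gap is narrow and partly covered elsewhere.

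- **Sodium.** Symptomatic 125-129 does have a grade. Protocol section 7.2 requires abnormal laboratory findings associated with signs or symptoms to be recorded as AEs, so a source for symptom status exists. Ungraded values remain in the observed-value and change summaries, the shifts against normal range and the listing of all abnormal values. Sodium is not among the Phase 2b laboratory parameters of special interest. All of this stands. What remains is that neither SAP links symptoms to a result and that the asymptomatic case has no cell.
- **AE onset.** The Phase 2b Introduction says the appendices are not a formal section of the signed SAP, and section 3.7.2 calls AEs observed before first dose non-treatment emergent, so the body arguably governs. But section 5.3 is the only detailed algorithm for onset, and section 3.7.3.1 itself cites an appendix, 5.8, as the grading source, so the appendices will be programmed. Setting onset to first dose is a defensible conservative default when the end date is unknown or falls after dosing. It is not defensible when the end date is known to precede dosing.
- **Consequence.** AE incidence is in general not tested in Phase 2b, the same rule applies in every arm, and the error adds TEAEs rather than hiding them. It also leaves a visible contradiction of end before onset that data review could catch.
- **QTcF.** Table 10 of the Phase 2b SAP (Table 6 of the Maintenance SAP) has a category of 430 and above for males, so the value is still counted there.

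**Conclusion.** All three gaps are wrong as written and of low impact. They do not touch efficacy, power or conduct. The AE error needs both a partial onset date in the month or year of first dose and a known end date before dosing. The sodium gap needs an asymptomatic value of 125-129, or one whose symptom status was not established. The documents do not give the number of such records.

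Two stronger readings are tempting and are not supported.

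1. A reader might conclude that the whole 125-129 band can never be graded. The table grades the symptomatic case as 3, and the AE record could supply symptom status; the SAPs only omit how to link it.
2. A reader might estimate that about half of screening AEs with a month-only onset are misfiled. With a 30-day month and first dose on day d, the part of a 28-day screening window in the same month is min(d - 1, 28)/28. Averaged over d = 1 to 30 this is (0 + 1 + ... + 28 + 28)/(30 x 28) = 434/840 = 0.517. That is the share of the window in the month of first dose, under uniform dates. It does not require the AE to have ended before dosing, so it includes AEs for which the missing check changes nothing. It is at most an upper bound for month-only onsets.

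**What to change.** - **Sodium, both SAPs:** fill the grade 2 cell with 125-129 mmol/L, asymptomatic or symptoms not recorded, after checking it against the CTCAE version 5.0 table that the SAPs name. State how symptom status is taken from the AE record, and write the bounds so that adjacent grades meet.
- **AE onset, Phase 2b SAP section 5.3:** add that if the AE end date is before first dose, a partial onset is imputed no later than the end date and the AE is not treatment-emergent. Reconcile section 5.3 with section 5.2.2.1 so that one rule governs partial onsets.
- **QTcF, section 3.7.3.3 of both SAPs:** define Normal for males as 430 msec or below.

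The cost is a few lines of SAP text and the matching programming. No new data and no change to trial conduct are needed.

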5.9. Multiple Imputation

Missing data after application of the appropriate intercurrent event strategy for (a) the primary estimand sensitivity analysis and (b) all supplementary estimand 1 analyses, is assumed missing

at random (MAR). A Multiple Imputation (MI) method will be used to impute missing data where the MI procedure will be used.

The MI procedure in the SAS Software is a multiple imputation procedure that creates multiply imputed data sets for incomplete p-dimensional multivariate data. It uses methods that incorporate appropriate variability across the m number of imputations. Once the m complete data sets are analyzed by using standard procedures, the MIANALYZE procedure can be used to generate valid statistical inferences about these parameters by combining results from the m complete data sets.

- The missing data are filled in m times to generate m complete data sets.
- The m complete data sets are analyzed by using standard procedures.
- The results from the m complete data sets are combined for the inference.

[figure not shown]
The following 5 step process will be followed for the primary estimand sensitivity analysis and all supplementary estimand 1 analyses:

[figure not shown]
1. To explore missing data patterns the MI procedure will be performed with 0 imputations and presented by treatment group for the following list of variables:
 - a. Prior biologic failure,
 - b. Corticosteroid use at enrolment,
 - c. Stool frequency, Rectal Bleeding and PGA scores at Baseline, Week 2, Week 4 and Week 8
 - d. Endoscopy score at Baseline and Week 8.

[figure not shown]
[Note: stratification factors and baseline variables are expected to be non-missing due to study eligibility criteria]

2. Generate 20 sets of imputed datasets separately for each treatment group using a fully conditional specification (FCS) with the logistic method (i.e. FCS LOGISTIC). The FCS statement will specify each of the total Mayo score components at Week 8 and both the CLASS and VAR statements will specify all variables listed in step 1.
3. The total Mayo score and respective change from baseline score will be calculated for each subject on each set of imputed datasets.
4. The statistical analysis plan specified ANCOVA model will be performed on each of the 20 imputed datasets.
5. Finally, the MIANALYZE procedure combines the results and provides valid statistical inferences.

STATISTICAL ANALYSIS PLAN

PHASE II-III

1. INTRODUCTION

This document outlines the plan for the summarization and analysis of clinical data collected in the Phase 3 Maintenance Study of Protocol 0157 for TD-1473.

Protocol 0157 comprises 3 separate studies within a single protocol. The purpose of multiple studies within a single protocol is to increase operational efficiency and reduce operational costs.

The 0157 maintenance study was terminated early due to lack of efficacy in the 0157 Phase 2b Induction study, all subjects date of last dose occurred by 11 September 2021 date and end of study visit by 20 October 2021 date.

The 0157 CSR will be an abbreviated CSR incorporating data from the Phase 2b Induction and Phase 3 Maintenance study and as a result all protocol defined analyses will not be performed.

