1.1. Objectives and Endpoints

1.1.1. Primary Objective(s) and Endpoint(s)

The primary objectives of the study are as follows:

- Assess the clinical remission rates associated with TD-1473 compared to placebo treatment at mWeek 44
- Assess the safety and tolerability of TD-1473 with up to 44 additional weeks of treatment

The primary endpoint is clinical remission by adapted Mayo score components at mWeek 44

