1.2. Study Design

This single protocol includes three studies: a Phase 2b dose-finding Induction Study, a Phase 3 dose-confirming Induction Study, and a Phase 3 randomized-withdrawal Maintenance Study (Figure 1).

Figure 1: Protocol Schema

* Estimated number of subjects for the re-randomized maintenance population

Each of the three studies will utilize a multi-center, randomized, double-blind, placebo-controlled, parallel-group design to evaluate various doses of TD-1473 compared to placebo in subjects with moderately-to-severely active ulcerative colitis (UC).

The Induction Studies will target subjects with moderately-to-severely active UC who demonstrate an inadequate response or failure to tolerate conventional or biologic therapy.

The Maintenance Study will be a randomized withdrawal study targeting subjects with moderately-to severely-active UC who demonstrate a clinical response to induction treatment with TD-1473.

Maintenance Study

In summary, subjects who demonstrate clinical response to a total of 8 weeks of TD-1473 induction therapy, either at Week 8 or Week 16, will be re-randomized. Those who demonstrate response to placebo at Week 8 or those who demonstrate response to a total of 16 weeks of TD-1473 treatment at Week 16 will enter the Maintenance Study on the same study drug treatment as during Induction for the purpose of maintaining blinding. The Maintenance Study consists of treatment for 44 weeks. During the Maintenance Study, subjects must taper their corticosteroid dose using the regimen outlined in Section 6.5.3 if they entered the study on corticosteroids.

The randomization will be stratified by clinical remission status at mWeek 0 using adapted Mayo score component definition, and corticosteroid use at enrollment into the Phase 3 Maintenance Study. In addition, randomization will also be stratified by subjects who reach clinical response after receiving 8 weeks of TD-1473 versus subjects who reach clinical response after receiving placebo during the first 8 weeks and then TD-1473 80 mg during extended induction.

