2. ANALYSIS SETS

Table 3: Analysis Sets

Analysis Set	Definition	Treatment Assignment
Safety	
The Safety analysis set will include all subjects who received at least one dose of study drug (TD-1473 or placebo) in the Maintenance study.
 
The Safety analysis set is the primary analysis set for safety analyses.
	Actual Treatment received
ITT	
The ITT set comprises all randomized into the Phase 3 Maintenance study.
 
Note: Subjects who demonstrate clinical response to a total of 8 weeks of TD-1473 induction therapy, either at Week 8 or Week 16 are eligible to be re-randomized into the maintenance study.
	Randomized treatment
mITT	
The mITT set comprises all randomized into the Phase 3 Maintenance study who were also treated.
 
Note: Subjects who demonstrate clinical response to a total of 8 weeks of TD-1473 induction therapy, either at Week 8 or Week 16 are eligible to be re-randomized into the maintenance study.
	Randomized treatment

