3.3. Primary Endpoint(s) Analysis

3.3.1. Definition of Primary Endpoint

The primary endpoint is:

- Clinical remission by adapted Mayo score components at mWeek 44

The adapted Mayo score (0-9 points) is the sum of three components: stool frequency (0-3 pts), rectal bleeding (0-3 pts), and Mayo endoscopic (0-3 pts) subscores.

Clinical remission by adapted Mayo score requires each of the subscores to meet the criteria defined in [Table 4](#). There will be no imputation of missing components, if a component is missing then the endpoint is missing.

Table 4: Clinical Remission by aMS Definition

Mayo Definition	Stool Frequency	Rectal Bleeding	Endoscopic Findings
Adapted Mayo Score (aMS)	0 or 1	0	0 or 1

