3.3.3. Main Analysis Methods

The proportions of subjects with clinical remission by aMS definitions will be compared between each TD-1473 treatment group and the placebo group using a fishers exact test.

Summaries of the proportion of subjects in remission will be presented by treatment group and p-values from the fishers exact test for the comparison of each dose of TD-1473 versus placebo.

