3.3.3.1. Missing Data Handling

There will be no imputation of missing data.

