3.4. Secondary Endpoint(s) Analyses

3.4.1. Definition of Secondary Endpoint(s)

As the study was terminated early only the following secondary endpoints will be analyzed:

- Endoscopic healing at mWeek 44
- Clinical response by adapted Mayo at mWeek44
- Symptomatic remission at mWeek44

Endoscopic Healing

Mayo endoscopic findings subscore ≤ 1 .

Symptomatic Remission

Symptomatic remission is defined as stool frequency subscore ≤ 1 and rectal bleeding subscore = 0.

Clinical Response by adapted Mayo score

Clinical response is defined as a reduction from baseline in adapted Mayo score of ≥ 2 points and $\geq 30\%$ relative to baseline. It also requires ≥ 1 reduction in the rectal bleeding subscore or an absolute subscore ≤ 1 .

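### The Maintenance mWeek 44 analysis labelled mITT is in effect an observed-case analysis: it drops treatment failures together with subjects cut off by termination, and Appendix 5.1 does not disclose this.

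*SAP*

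**What the plan says.** The Maintenance SAP, section 1, says the study was terminated early for lack of efficacy in the Phase 2b Induction Study and that "all subjects date of last dose occurred by 11 September 2021 date and end of study visit by 20 October 2021 date". Section 1.2 still describes the full design: "The Maintenance Study consists of treatment for 44 weeks". Section 1.1.1 keeps the time point: "The primary endpoint is clinical remission by adapted Mayo score components at mWeek 44".

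The population is set in section 2: "The mITT set comprises all randomized into the Phase 3 Maintenance study who were also treated". Section 3.3.2 names mITT for the primary endpoint, and section 3.3.3 gives the method, Fisher's exact test for each dose: "The proportions of subjects with clinical remission by aMS definitions will be compared between each TD-1473 treatment group and the placebo group". Section 3.4.1 keeps three secondary endpoints at mWeek 44 (endoscopic healing, clinical response and symptomatic remission), and section 3.4.3 analyses them in the same way.

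Missing data are covered twice. Section 3.3.1: "There will be no imputation of missing components, if a component is missing then the endpoint is missing". Section 3.3.3.1: "There will be no imputation of missing data". Section 3.4.3.1 applies the same rule to the secondary endpoints, and section 3.3.4 rules out sensitivity analyses.

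The protocol says otherwise. Sections 8.5.4 and 8.9 count a subject with missing data, or one who meets a treatment failure criterion, as not in remission. Maintenance SAP Appendix 5.1 lists the deleted endpoints and the move from CMH to Fisher's exact test as the major changes. It does not list the dropped missing-data rule.

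**The concern.** In this study an mWeek 44 result can be absent for two quite different reasons. One is administrative: the sponsor stopped dosing before the subject reached mWeek 44. The other is outcome-related. Under protocol section 6.3.12, a subject with no improvement at CFA Visit 3, or with a second Clinical Flare after loss of response, is taken off study drug. That subject then leaves without an mWeek 44 visit because treatment failed.

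The SAP treats both as missing and removes both. What remains is the remission rate among subjects who entered early enough and did not fail on the way. That is not a 44-week remission rate in the re-randomised, treated population, although it carries the mITT label. In a randomised-withdrawal design, failure exits may also differ between placebo and active, so the distortion need not cancel. These are the mWeek 44 efficacy figures that this SAP supplies for the abbreviated CSR.

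**Working it through.** **1. The plan's own figures.** The only remission rates in the documents are the design assumptions in Maintenance SAP section 1.5: 15% on placebo, 30% and 40% on active, 120 per group, Hochberg at two-sided 5%. Simulating 200,000 three-arm trials gives 99.0% disjunctive power (stated: at least 90%) and 80.4% conjunctive power (stated: 80%). The stated power reproduces. I use 15% and 40% below only as illustrative true rates.

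**2. Who could reach mWeek 44.** Inputs: latest last dose 11 September 2021 (SAP section 1); 44 weeks = 44 × 7 = 308 days; visit window -3 to +2 days (protocol Table 2).

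- 11 September 2021 - 308 days = 7 November 2020.
- 11 September 2021 - 305 days = 10 November 2020, using the -3 day edge.

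This is the most lenient cut-off, because 11 September is the latest last-dose date over all subjects. Anyone stopped earlier by the sponsor needed an earlier start.

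**3. Whether early leavers have a result.** Table 2 schedules endoscopy at mWeek 44 and not at the Early Study Drug Discontinuation visit. Flare endoscopy (CFA Visit 2) is not an mWeek 44 assessment. A subject who stops before mWeek 44 therefore generally has no remission status there, and sections 3.3.1 and 3.3.3.1 leave the endpoint missing.

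**4. What removing failures does.** Let r be the true 44-week remission rate among subjects with time to reach mWeek 44, and e the share of them who leave through failure. Assume that none of the leavers would have counted as in remission and that all others have a result. Then

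reported rate = r / (1 - e).

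The documents give no value for e, so the exit shares are assumptions, as are the true rates in the last row:

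| True placebo / active | Exit placebo / active | Reported placebo / active | Reported difference |
|---|---|---|---|
| 15% / 40% | 0% / 0% | 15.0% / 40.0% | 25.0 points |
| 15% / 40% | 50% / 25% | 0.15/0.50 = 30.0% / 0.40/0.75 = 53.3% | 23.3 points |
| 15% / 40% | 25% / 25% | 0.15/0.75 = 20.0% / 0.40/0.75 = 53.3% | 33.3 points |
| 15% / 40% | 50% / 10% | 0.15/0.50 = 30.0% / 0.40/0.90 = 44.4% | 14.4 points |
| 15% / 15% | 50% / 50% | 0.15/0.50 = 30.0% in each arm | 0 points |

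Wherever failures leave, the level rises. The difference can shrink, grow or stay put, depending on how exits split by arm. The last row shows that the level can double even when the drug has no effect.

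**5. What removing cut-off subjects does.** Entry date precedes Maintenance outcome. Within the concurrent 1:1:1:1 re-randomisation that applied before dose selection (protocol section 3.1), it is unrelated to arm. Removing everyone who entered too late therefore costs sample size but does not by itself bias the comparison. The bias comes from removing failures among those who had the time.

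**The case against.** A reader might infer something stronger: that the SAP formally tests mWeek 44 remission in every re-randomised treated subject, with those cut off counted as non-remitters. If 45% could not reach mWeek 44 (assumption), 15% and 40% would then shrink to 0.15 × 0.55 = 8.25% and 0.40 × 0.55 = 22.0%. The documents do not support this. Sections 3.3.1 and 3.3.3.1 leave the endpoint missing, so a cut-off subject has no value to enter. Sections 3.3.2, 3.4.2 and 3.5 say that the study is not powered, that p-values are descriptive and that there is no hypothesis testing.

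On the point as made here, the best defence has four parts.

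- For cut-off subjects, the SAP already does roughly what an entry-date restriction would do. This stands. The defect is confined to subjects who had the time and failed.
- Under the 50%/25% assumption the difference barely moves (23.3 against 25 points). True for that pair, but other splits move it considerably, and the levels are wrong in every row with exits.
- The disposition table (section 3.2.1) gives early discontinuations by treatment with primary reasons, and protocol section 6.6.1 lists sponsor termination as a reason. This helps a careful reader, but it does not change the reported proportions or give their denominators.
- This is a terminated study in an abbreviated report, with no confirmatory claim. That limits the consequence. A descriptive rate should still describe what its label says.

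**Conclusion.** The concern holds in this limited form. Followed as written, the Maintenance SAP produces an observed-case mWeek 44 analysis under the mITT name. It departs from the protocol's rule that missing counts as not in remission, does not state its denominators, and does not list the departure in Appendix 5.1. To the extent that subjects left through failure, the reported 44-week rates are too high, and unequal exits would also distort the difference between arms.

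The size cannot be derived, because neither Maintenance entry dates nor exit rates are given. The 30% against 53% illustration rests on assumed exits of 50% and 25% and on design rates that may not apply to a study stopped for lack of efficacy. The 7 to 10 November 2020 dates are firm as arithmetic, but only as the most lenient limit. No formal inference is affected; what is affected is the meaning of the descriptive rates. The change is worth making because it is cheap.

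**What to change.** In Maintenance SAP section 2, add a set of mITT subjects whose first Maintenance dose was at least 305 days (308 less the 3-day window) before the date on which sponsor-termination stops began. Use one calendar date for all arms: the earliest such stop, not 11 September 2021. With the latest last-dose date as the limit, a subject stopped by the sponsor some weeks earlier could fall inside the set and be counted as a failure.

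In that set, report mWeek 44 remission and the three retained secondary endpoints with missing counted as not met, as in protocol sections 8.5.4 and 8.9. Keep the existing analysis, but label it observed-case and show the denominator for each arm. Report the number of mITT subjects outside the new set by arm. Add the missing-data change to Appendix 5.1.

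The cost is one flag from dates that the trial should already hold, one extra run of four endpoints and a short paragraph. The downside is a smaller denominator, including the loss of a few later entrants who did reach mWeek 44 because they were stopped after the earliest date; they remain in the observed-case table.
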